9.2 Handling of Serious Adverse Events (SAEs)

9.2.1 SAE Definitions

A **serious AE** is any untoward medical occurrence occurring after initiation of study treatment or that at any dose:

- results in death
- is life-threatening (defined as an event in which the study patient was at risk of death at the time of the event; it does not refer to an event which hypothetically might have caused death if it were more severe)
- requires inpatient hospitalization or causes prolongation of existing hospitalization
- results in persistent or significant disability/incapacity
- is a congenital anomaly/birth defect
- is suspected transmission of an infectious agent (e.g., pathogenic or nonpathogenic) via the study drug
- is an important medical event (defined as a medical event(s) that may not be immediately life-threatening or result in death or hospitalization but, based upon appropriate medical and scientific judgment, may jeopardize the patient or may require intervention (e.g., medical, surgical) to prevent one of the other serious outcomes listed in the definition above).

Examples of such events include, but are not limited to, intensive treatment in an emergency room or at home for allergic bronchospasm; blood dyscrasias or convulsions that do not result in hospitalization.

9.3 SAE Reporting Requirements

Serious adverse events (SAE) are defined above. The investigator should inform PrECOG of any SAE within 24 hours of being aware of the event. The date of awareness should be noted on the report. This must be documented on the PrECOG SAE form. This form must be completed and supplied to PrECOG within 24 hours/1 business day at the latest on the following working day. The initial report must be as complete as possible, including details of the current illness and (serious) adverse event, and an assessment of the causal relationship between the event and the investigational product(s). Information not available at the time of the initial report (e.g., an end date for the adverse event or laboratory values received after the report) must be documented on a follow-up PrECOG SAE report form. A final report to document resolution of the SAE is required. The investigator is responsible

for following all SAEs until resolution, until the subject returns to baseline status, or until the condition has stabilized with the expectation that it will remain chronic, even if this extends beyond study participation. A copy of the transmission confirmation of the SAE report to PrECOG should be attached to the SAE and retained with the patient records.

SAEs should be scanned and emailed to [contact] as per the instructions found in study materials provided to the investigator site.

██████████
Medical Monitor
During normal business hours
(8:30 am-5:00 pm EST):
[contact]
After normal business hours:
[contact]
Email: ██████████

Manager, Clinical Safety
During normal business hours
(8:30 am-5:00 pm EST):
[contact]
After normal business hours:
[contact]

PrECOG will notify BMS or designee of all SAE's within 24 hours of PrECOG's & Investigator's Awareness Date as discussed above. Relevant follow-up information will be provided to BMS as soon as it becomes available. In addition, every 3 months PrECOG will send BMS a listing of all non-serious events (only adverse events not previously submitted).

Investigators should also report event(s) to their IRB as required.

Collection of complete information concerning SAEs is extremely important. Full descriptions of each event will be followed. Thus, follow-up information which becomes available as the SAE evolves, as well as supporting documentation (e.g., hospital discharge summaries and autopsy reports), should be collected subsequently, if not available at the time of the initial report, and immediately sent using the same procedure as the initial SAE report.

All SAEs, regardless of causality, must be collected which occur within 100 days of last dose of study treatment. This includes all deaths within 100 days of last dose of nivolumab and/or lirilumab regardless of attribution. In addition, the Investigator should notify PrECOG or designee of any SAE that may occur after this time period which they believe to be definitely, probably or possibly related to investigational product.

NOTE: After study closure, study-drug related SAEs should be reported voluntarily by the treating physician to the manufacturer.

Serious adverse event reporting to regulatory authorities and all participating investigators will be conducted by PrECOG (or designee) in accordance with 21CFR312.32, local requirements and international regulations, as appropriate. FDA reporting requirement timelines will be followed. PrECOG will also concurrently forward any such reports to BMS.

9.4 Potential Drug-Induced Liver Injury

All occurrences of potential drug-induced liver injury, meeting the defined criteria below, must be reported as SAEs.

- ALT or AST elevation >3 times upper limit of normal (ULN)

AND

- Total bilirubin >2 times ULN, without initial findings of cholestasis (elevated serum alkaline phosphatase)

AND

- No other immediately apparent possible causes of ALT or AST elevation and hyperbilirubinemia, including, but not limited to, viral hepatitis, pre-existing chronic or acute liver disease, or the administration of other drug(s) known to be hepatotoxic.

9.5 Reporting of Other Second Primary Cancers

New cancers are those that are not the primary reason for administration of study treatment and have been identified after inclusion of the patient into the clinical study.

All cases of new primary cancers that occur during or after protocol treatment must be reported to PrECOG on a Second Primary Cancer form within 30 days of diagnosis, regardless of relationship to protocol treatment. Secondary primary malignancies should also be reported as a SAE. The SAE form is not for use for reporting recurrence or development of metastatic disease. A copy of the pathology report, if applicable, should be sent, if available.

NOTE: Once data regarding survival and remission status are no longer required by the protocol, no follow-up data should be submitted.

9.6 Procedures in Case of Pregnancy

Prior to study registration, women of childbearing potential (WOCBP) and male patients with a female partner of childbearing potential must be advised of the importance of avoiding pregnancy during trial participation and the potential risk factors for an unintentional pregnancy, documented in the informed consent. In addition, all WOCBP should be instructed to contact the Investigator immediately if they suspect they might be pregnant (e.g., missed or late menstrual period) at any time during study participation.

Pregnancy of a female patient or the female partner of a male patient occurring while the patient is receiving study drug or within 5 months after a female patient's last dose of study drug or 7 months for the female partner of a male patient's last dose of study drug will be reported to PrECOG on a SAE Form within 24 hours of the investigator's knowledge of the pregnancy.

All reports of congenital abnormalities/birth defects and spontaneous miscarriages should also be reported and handled as SAEs. Elective abortions without complications should not be handled as AEs.

The outcome of all pregnancies (spontaneous miscarriage, elective termination, normal birth including health of the newborn or congenital abnormality) must be followed and documented on the Pregnancy Form even if the subject was discontinued from the study treatment. Should pregnancy occur during a subject's participation, the subject will immediately be discontinued from the treatment and followed per protocol.

The SAE Form can be found in the Study Reference Manual. A study specific Pregnancy Form will also be completed.

9.7 Reporting Guidelines in the Case of Overdose

Any overdose of a study subject with nivolumab and/or lirilumab, with or without associated AEs/SAEs, is required to be reported within 24 hours of knowledge of the event to PrECOG. If the overdose results in an AE, the AE must also be recorded as an AE. Overdose does not automatically make an AE serious, but if the consequences of the overdose are serious, for example death or hospitalization, the event is serious and must be recorded and reported as an SAE. There is currently no specific treatment in the event of an overdose of nivolumab and/or lirilumab.

10. Measurement of Effect

Patients should be evaluated for pathologic tumor response at post-treatment radical cystectomy time point. Progression will be evaluated in this study using the new international criteria proposed by the revised Response Evaluation Criteria in Solid Tumors (RECIST) guideline Version 1.1 (Appendix IV).⁴⁶ RECIST response assessments will be performed locally for the trial.

10.1 Evaluable Population Definitions

Evaluable for Toxicity: All patients will be evaluable for toxicity from the time of their first treatment with nivolumab and/or lirilumab.

Evaluable for Tumor Response: Only those patients who have received at least one dose of therapy, and undergo radical cystectomy will be considered evaluable for tumor response. These patients will have their tumor response classified according to the definitions stated below. (**NOTE:** Patients who exhibit objective disease progression prior to the end of treatment will also be considered evaluable.)

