- 14 Radical cystectomy with bilateral (standard or extended) pelvic lymph node dissection to be performed as soon as possible but within 6 weeks after the last neoadjuvant infusion.

- 15 Obtain CTs (or MRI as noted above) after second dose of nivolumab +/- lirilumab and before surgery.

- 16 Thirty (30) days +/- 7 days after cystectomy. If patient is removed from treatment for reason(s) other than progression, follow with regular tumor assessments per standard of care until progression or start of new treatment. Once a patient has initiated a new therapy, no further imaging assessments for this study are required.

NOTE: If cystectomy is not performed, Off Treatment visit should be performed at next scheduled appointment or treating physician discretion, as clinically indicated.

- 17 Patients will be followed for adverse events for 100 days after their last dose of neoadjuvant therapy. Adverse events may be reviewed at the next visit \geq 100 days after last dose of neoadjuvant therapy or phone follow-up may be done to review adverse events. However, an adverse event occurring at any time after discontinuation of study therapy that is felt to be at least possibly related to study therapy should be recorded.

- 18 Patients will be followed clinically and radiographically per standard of care (every 3-6 months) at the discretion of the treating physician for at least 2 years post-cystectomy or when study-wide follow-up ends. Date of diagnosis for progression, first subsequent therapy and survival shall be reported. Phone follow-up may also be done for patients unable or unwilling to return for follow-up evaluations.

12. Drug Formulation and Procurement

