13.2.3.1 Analytic Plan for Additional Secondary Objectives

1. The mean percent change of CD8+ TIL density from pre-treatment (TURBT) to post-treatment (radical cystectomy) samples in all 12 patients in Cohort 1 and all 24 patients in Cohort 2 will be calculated

and compared between the two cohorts using a Wilcoxon rank sum test.

2. The proportion of patients in each treatment cohort who do not get radical cystectomy specifically and directly related to treatment related AEs within 6 weeks of the completion of neoadjuvant treatment, will be reported along with exact binomial 90% confidence intervals for each cohort and compared between the two cohorts using Fisher's exact test.
3. The proportion of patients in each treatment cohort with pathologic complete response (CR) and pathologic partial response (PR) will be reported along with exact binomial 90% confidence intervals for each cohort.
4. Recurrence-free survival (defined as patients who are alive and without evidence of disease recurrence) from the time of registration will be estimated using Kaplan-Meier method for each treatment cohort and compared between the two cohorts using a log-rank test. One-year and two-year disease-free survival estimates and confidence intervals will be provided for each cohort.

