### 5.6. Recurrence-Free Survival (RFS) as per RECIST 1.1

Recurrence is defined as the Progressive Disease (PD) in Overall Response assessed by ERECIST 1.1 or death after radical cystectomy. RFS time is defined as the duration of time from start of treatment to time of first documented recurrence (after radical cystectomy) or death, whichever occurs first.

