### **7.5.2. Efficacy Population**

The efficacy population is defined as all patients who received at least one dose of trial therapy, undergo radical cystectomy and have at least one of the following tumor evaluations listed below. Patients who exhibited objective disease recurrence prior to the end of treatment will also be considered as part of the efficacy population.

Below is the list of tumor evaluations:

1. CD8+ T-Cell Density

2. %CD8+ Tumor-Infiltrating T-Cells
3. Pathologic Tumor Response
4. Tumor IHC Staining Intensity Definitions

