### **7.7. Efficacy Analysis**

All Efficacy analyses are performed for efficacy population except Recurrent-Free Survival and Overall Survival analyses. The RFS and OS analyses are performed for safety population.

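### Pathologic response is analysed among operated patients, so treated patients who miss cystectomy can drop out of the denominator and raise the rate

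*Protocol*

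**What the plan says.** Protocol 13.2.3.1, item 3, reports "The proportion of patients in each treatment cohort with pathologic complete response (CR) and pathologic partial response (PR"), each with an exact 90% binomial interval. SAP 7.4.2.4 says the same. Neither names a denominator other than the cohort.

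The population definitions are narrower:

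- Protocol 10.1: "Only those patients who have received at least one dose of therapy, and undergo radical cystectomy will be considered evaluable for tumor response". A note adds: "Patients who exhibit objective disease progression prior to the end of treatment will also be considered evaluable".
- SAP 5.1 repeats the cystectomy condition without the note.
- SAP 7.5.2 defines the efficacy population as patients with at least one dose who "undergo radical cystectomy and have at least one of the following tumor evaluations listed below", and adds: "Patients who exhibited objective disease recurrence prior to the end of treatment will also be considered as part of the efficacy population".
- SAP 7.7: "All Efficacy analyses are performed for efficacy population except Recurrent-Free Survival and Overall Survival analyses". Those two use the safety population, which is every patient given at least one dose (SAP 7.5.1).

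Response, complete response and non-response are all defined from the cystectomy stage (Protocol 10.5; SAP 5.4 and 7.7.3). For pre-surgical imaging, Protocol Section 11, footnote 15, says: "Obtain CTs (or MRI as noted above) after second dose of nivolumab +/- lirilumab and before surgery".

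**The concern.** Whether a patient reaches surgery is settled after treatment starts and can depend on the treatment. Both documents foresee missed surgery. They say when the off-treatment visit takes place if cystectomy is not done (Protocol 5.3; SAP 4.1), and they make non-surgery due to treatment-related adverse events a secondary endpoint. Protocol 5.2 replaces patients only for a late start, no dose or inadequate tumour content, so a treated patient who is not operated on is not replaced. That patient simply leaves the response denominator.

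Pathologic response is the plan's stated measure of antitumour efficacy (Protocol 2.2). A rate among operated patients answers a different question from a rate among patients who started the regimen, and the plan's own wording points to the second. If the denominator is left unsettled, it may be chosen once it is known who missed surgery, in an open-label trial where one patient is 1/12 = 8.3 percentage points of Cohort 1.

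**Working it through.** **Inputs.** N = 12 and N = 24 treated patients (Protocol 13.2.2.1; SAP 7.1). Exact 90% intervals (Protocol 13.2.3.1). The documents give neither the number not operated on nor an expected response rate, so k and x below are assumptions. Here k is the number of treated patients who have no cystectomy and are not kept by the progression exception, and x is the number of responders.

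**Reproducing the plan's figure.** Protocol 13.2.1.1 gives maximum interval widths of 0.51 and 0.36 for the primary endpoint; the response rates use the same method. Clopper-Pearson limits are the 5% quantile of Beta(x, n − x + 1) and the 95% quantile of Beta(x + 1, n − x). The width peaks at 0.509 for n = 12 (x = 6) and 0.361 for n = 24 (x = 12). Both match.

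**Effect of the denominator.** Operated-only rate = x/(N − k). All-treated rate, with no specimen counted as no response, = x/N. Ratio = N/(N − k), which does not depend on x and is never below 1.

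| Not operated on | Cohort 1 (N = 12) | Cohort 2 (N = 24) | Ratio |
|---|---|---|---|
| 0% | k = 0 | k = 0 | 1.00 |
| 8% | k = 1: 12/11 | k = 2: 24/22 | 1.09 |
| 17% | k = 2: 12/10 | k = 4: 24/20 | 1.20 |
| 25% | k = 3: 12/9 | k = 6: 24/18 | 1.33 |

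Examples with assumed responder counts (90% intervals):

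| N, k, x | Operated only | All treated | Excess, points |
|---|---|---|---|
| 12, 1, 2 | 2/11 = 18.2% (3.3 to 47.0) | 2/12 = 16.7% (3.0 to 43.8) | 1.5 |
| 12, 2, 3 | 3/10 = 30.0% (8.7 to 60.7) | 3/12 = 25.0% (7.2 to 52.7) | 5.0 |
| 24, 4, 8 | 8/20 = 40.0% (21.7 to 60.6) | 8/24 = 33.3% (17.8 to 52.1) | 6.7 |
| 24, 6, 8 | 8/18 = 44.4% (24.4 to 65.9) | 8/24 = 33.3% (17.8 to 52.1) | 11.1 |

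Over responder shares of 17% to 33% and 8% to 25% not operated on, the excess is about 1.5 to 11 points.

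Unequal surgery completion also separates the cohorts without any difference in response. Take 25% responders among treated patients in both: 3/12 = 25% if all of Cohort 1 is operated on, against 6/20 = 30% if four of Cohort 2 are not.

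**How far the exception helps.** Each progressor it keeps reduces k by one. If two of four unoperated patients in Cohort 2 are kept, 8 responders give 8/22 = 36.4%, between 33.3% and 40.0%. Whether they are kept is not settled, for three reasons:

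1. End of treatment is not defined. The restaging scan follows the second and last dose. If treatment ends with that dose, progression first seen on the scan falls outside the exception; if it ends at the off-treatment visit, it falls inside.
2. The protocol says progression; SAP 7.5.2 says recurrence. SAP 5.6 equates recurrence with RECIST progressive disease, but also times the recurrence-free survival event as "time of first documented recurrence (after radical cystectomy) or death". On the first sense the exception works as in the protocol. On the second it adds nobody: such patients have already had cystectomy.
3. SAP 5.1 has no exception at all.

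On any reading, toxicity, death without objective progression, refusal and clinical decline stay outside the exception.

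**The case against.** Much of the case on the other side stands.

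- **The protocol does not restrict the set to operated patients alone.** Its note keeps objective progressors. The remaining gap is the other reasons for missing surgery, plus the unclear boundary of the note.
- **A reader might infer that the SAP turned the exception into an event that cannot occur.** The documents do not support that. SAP 5.6 equates recurrence with progressive disease, SAP Section 5 uses recurrence where Protocol Section 10 uses progression, the SAP document history records a similar terminology change, and SAP Section 8 declares no change from the protocol. The wording is ambiguous, and empty on only one reading.
- **A reader might infer that progression on the restaging scan is always excluded.** That assumes treatment ends with the last dose. SAP 6.4 lists an examination at end of treatment after the one at surgery, and the schedule places the last examination at the off-treatment visit about 30 days after cystectomy. Protocol 6.1.3 puts cystectomy inside the treatment plan. The term needs a definition.
- **A kept progressor without a non-response label does not distort the rate.** That patient is in the denominator and not in the numerator either way.
- **The endpoint carries limited weight.** The primary endpoint is safety and the key secondary is the change in CD8+ density. Pathologic response has no hypothesis, power or decision rule, and no between-cohort test.
- **The gap is partly visible.** SAP 7.6.1, 7.6.5 and 7.6.6.2 report disposition, the number having cystectomy and adverse-event-related non-surgery, so a reader could divide responders by treated patients.
- **Without a specimen, response is unknown.** Counting it as not achieved is conservative.

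These points lower the severity. They leave in place a headline rate conditioned on a post-treatment event, beside text that describes the cohort.

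**Conclusion.** The point holds as a should-fix. As written, pathologic response is analysed in a population that requires cystectomy, apart from an exception of uncertain reach. Relative to all treated patients, the rate can be raised and never lowered. The factor is N/(N − k): 1.09 to 1.33 if 8% to 25% of treated patients are not operated on and not kept by the exception. Those shares are assumptions, because neither document gives a surgery-completion rate.

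It would go too far to say that the reported rates are inflated as a matter of fact. If every treated patient has cystectomy, the two rates coincide, and fitness for cystectomy is an entry criterion (Protocol 3.4). It would also go too far to call this a must-fix in the trial's main efficacy result, since the endpoint is a descriptive additional secondary one. In the tabulated examples the 90% intervals for the two denominators overlap heavily.

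**What to change.** In Protocol 10.1 and 13.2.3.1 and SAP 5.1, 7.5.2 and 7.7.3:

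- Report pathologic complete response and <pT2N0 with all treated patients as the main denominator. This is the SAP safety population, already used for recurrence-free and overall survival.
- Count a treated patient without a cystectomy specimen, for whatever reason, as not achieving pathologic response.
- Give the operated-only rate as supportive, with its own denominator shown.

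In SAP 7.5.2, use progression in place of recurrence, as in the protocol, and tie the exception to the period before cystectomy instead of an undefined end of treatment. Make Protocol 10.1 and SAP 5.1 agree with it.

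The cost is wording in both documents and one extra table; no new data are needed. The main rate becomes slightly less favourable and is conservative, because response is unknown without a specimen. The supportive rate shows how much that choice matters.

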10.2 CD8+ T-Cell Density

The CD8+ T-cell density is defined as the number of CD8+ tumor-infiltrating T-cells per 100 tumor cells within a 400x high power field (HPF). The CD8+ T-cell density will be calculated as:

Tumor Infiltrating CD8+ T-cell density (CD8+ T-cells per 100 tumor cells) =
(Total # of CD8+ TILS)/ (Total # of tumor cells per HPF) x 100

Five representative tumor fields with the greatest gross tumor infiltrating lymphocyte fields (minimum 100 tumor cells per representative field) will be chosen for measurement by microscope analysis by the pathologist with the final CD8+ T-cell density determined as the mean of the CD8+ T-cell density across the five fields.

10.3 %CD8+ Tumor-Infiltrating T-Cells

The %CD8+ tumor-infiltrating T-cells will be quantified by immunohistochemistry (IHC) analysis of tissue. Using semi-automated image analysis, a staining percentage determined by dividing the area of brown 3,3'-Diaminobenzidine (DAB) staining by the area of epithelial cells will be obtained.

Five representative tumor fields with the greatest gross tumor infiltrating lymphocyte fields will be chosen for measurement by the pathologist with the final %CD8+ tumor-infiltrating T-cells determined as the mean of the %CD8+ tumor-infiltrating T-cells across the five fields.

